
	
weights for the primary OS are <math>w = \sqrt{231/345}</math> and <math>1-w</math> for events occurring before and after the second interim analysis, respectively. The middle point, 345, of minimum and maximum event sizes is chosen to set up the weights. The conventional stratified log-rank test with equal weights for every patient will be conducted as a sensitivity analysis. Details will be provided in the Statistical Analysis Plan.
 
Safety:
 
Overall safety and tolerability of bempegaldesleukin plus pembrolizumab will be measured by the incidence of AEs, AESIs, SAEs, deaths, and laboratory abnormalities. Safety analyses will be summarized for the Safety population using descriptive statistics by treatment arm.

--	---

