**11.2.2 Sample Size Justification for OS**

The study is powered to detect an improvement in OS for bempegaldesleukin combined with pembrolizumab compared with pembrolizumab monotherapy. An initial total of 298 OS events are needed to detect a hazard ratio (HR) of 0.7 with 85% power at a 2-sided significance level of 0.049. Assuming a median OS time for the pembrolizumab arm of 12.3 months (Burtness 2019), with a total sample size of 500, it is projected the total study duration is up to 52 months to reach 393 OS events (after an initial varying staged incremental accrual in the first 5 months to 35 patients per month, then a 4-month enrollment pause after 200 patients have been randomized

and resumed at an initial varying staged incremental accrual in the first 3 months to 35 patients per month until 500 patients are randomized).

One interim analysis of OS is planned for this study at IA2. The interim analysis is projected to occur at 32 months from the first patient randomized into the study. The stopping boundaries at interim and final analyses will be derived based on the number of deaths using O'Brien and Fleming alpha spending function in software EAST 6.5. The detailed alpha spending and statistical significance level at each analysis below are for the planned number of events. If the actual number of events at the time of the analysis is different from the planned one, the actual alpha and statistical significance level will be adjusted using O'Brien and Fleming alpha spending function in software EAST 6.5.

There are two possible testing scenarios at IA2 for OS:

1. The ORR difference is statistically significant at IA2 at alpha level of 0.001.

The overall Type I error rate is 0.05 for the primary endpoint OS and OS will be tested at alpha level of 0.022 at IA2. If the observed HR is tested statistically significant in favor of the combination of treatments, OS benefit will be concluded. Otherwise, OS will be tested at alpha level of 0.028 at the final analysis (FA) corresponding to the statistical significance level of 0.044 calculated based on the correlation of the interim and final combination test statistic.

2. The ORR difference is not statistically significant at IA2.

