The overall Type I error rate is 0.049 for the primary endpoint OS. OS will be tested at alpha level of 0.021 at IA2. If the observed HR is tested statistically significant in favor of the combination of treatments, then OS benefit will be concluded. Otherwise, the HR will be tested at alpha level of 0.029 at the final analysis corresponding to the statistical significance level of 0.043 calculated based on the correlation of the interim and final combination test statistic.

The detailed calculation will be provided in the SAP.

At IA2, if OS is not statistically significant, then conditional power will be calculated. The adaptive method in Liu and Hu ([Liu 2016](#)) and Mehta and Pocock ([Mehta 2011](#)) will be used to determine the number of OS events needed to target approximately 85% to 90% conditional power for the final analysis. The final analysis will be triggered when this re-estimated number of OS events is reached.

The minimum and maximum number of OS events for the final analysis are 298 and 393, respectively. The minimum event size is calculated to achieve 86% power with  $\alpha = 0.049$  (two-sided) assuming an exponential distribution in each treatment arm and an HR = 0.7 with median OS for the pembrolizumab arm of 12.3 months ([Burtness 2019](#)). The maximum event size is determined to detect the minimum clinically meaningful effect of HR around 0.82.

The detailed sample size adaptation rules based on conditional power will be described in an appendix of the Data Monitoring Committee (DMC) Charter, which will not be accessible to the study team or sites to prevent introduction of any potential bias; however, the operational procedures will be described in the DMC Charter, which is accessible to the study team.

The key secondary endpoints will be tested hierarchically given statistical significance of OS. Further details of the testing procedure will be described in the SAP.

Figure 2 provides the study flow and decision-making time points for the primary endpoints.

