If the DMC determines that the study should continue based on the prespecified futility boundary, Phase 3 of the study will begin following a projected 4-month enrollment pause for the first interim analysis readout. At the second interim analysis when approximately 500 patients have been randomized and about 231 overall survival events have been observed, the following tests will be conducted:

- ORR will be tested at a statistical significance level of 0.001 at the second interim analysis.
- If ORR is not significant at the second interim analysis, overall survival will be tested at an overall alpha level of 0.049 and at  $\alpha = 0.021$  at the second interim analysis.
- If ORR is significant at the second interim analysis, the fallback method will be used, and overall survival will be tested at an overall alpha level of 0.05 and at  $\alpha = 0.022$  at the second interim analysis.

At the final analysis, the primary analysis of overall survival to claim statistical significance will be based on the weighted combination version of the stratified log-rank test with prespecified

weights (Lehmacher 1999). Statistical significance level for the final analysis is 0.043 or 0.044 depending on whether ORR is significant at the second interim analysis. Prespecified weights for the primary OS are  $w = \sqrt{231/345}$  and  $1-w$  for events occurring before and after the second interim analysis, respectively. The middle point, 345, of minimum and maximum event sizes is chosen to set up the weights. The conventional stratified log-rank test with equal weights for every patient will be conducted as a sensitivity analysis. Details will be provided in the SAP.

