2.0 ANALYSIS PLAN

One patient was enrolled and treated in this study. No summary will be produced, instead, individual patient level listings with the following data will be provided.

Patient disposition, demographics and baseline characteristics will be described using listings of individual patient data. Patient demographics and baseline characteristics will include age, gender, ethnicity, race, geographic region, disease stage, primary tumor location, and disease status (metastatic vs recurrent only), PD-L1 tumor expression (CPS \geq 20 vs CPS 1-19), and HPV status (positive or negative), as applicable.

Prior and concomitant medications and therapies will be described using listings of individual patient data.

Adverse events (AEs) collected in the study will be described using AE listings including AE start and end dates, grade, relatedness to study drug, action taken and AE outcome. Adverse events will be coded by system organ class (SOC) and preferred term (PT) using MedDRA version 24.0. Adverse event severity will be based on National Cancer Institute Common Terminology Criteria for Adverse Events (NCI CTCAE) Grade (version 5.0). An AE is considered as related to treatment if it is related to any study drug; an AE with a missing relationship will be counted as related to study drug. An AE is considered as leading to treatment discontinuation if it is leading to discontinuation of any study drug. An AE is considered as leading to death if the severity grade is 5 or the outcome is fatal.

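### The final OS test is mis-specified: the weights sqrt(231/345) and 1-w do not give unit variance, and the final levels 0.043/0.044 belong to 298 events, not 345

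*Protocol*

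**What the plan says.** Protocol Section 11.5.1 makes a weighted combination of stratified log-rank statistics the test that decides OS significance at the final analysis. The synopsis (Statistical Methods) states: "weights for the primary OS are w = \sqrt{231/345} and 1-w for events occurring before and after the second interim analysis, respectively". Section 11.5.1 repeats the formula and explains the 345: "for events occurring before and after the second interim analysis, respectively. The middle point, 345, of minimum and maximum event sizes is chosen". The minimum and maximum final event counts are 298 and 393.

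Section 11.5.1 also fixes the final level: "Statistical significance level for the final analysis is 0.043 or 0.044 depending on whether ORR is significant at the second interim analysis". Section 11.2.2 says where it comes from. If ORR is significant, it is "the statistical significance level of 0.044 calculated based on the correlation of the interim and final combination test statistic"; if not, it is the "statistical significance level of 0.043 calculated based on the correlation of the interim and final combination test statistic". The matching IA2 levels are 0.022 and 0.021, spent from overall two-sided OS alphas of 0.05 and 0.049 by an O'Brien-Fleming spending function.

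On power, Section 11.2.2 says: "An initial total of 298 OS events are needed to detect a hazard ratio (HR) of 0.7 with 85% power". Later in the same section: "The minimum event size is calculated to achieve 86% power".

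The protocol leaves the details to the SAP. SAP Section 2.0 provides listings only, because "One patient was enrolled and treated in this study".

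**The concern.** Two separate parts of the final test do not fit.

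**Weights.** A sum w1·Z1 + w2·Z2 of independent stage-wise statistics is standard normal under the null only if w1² + w2² = 1. With w1 = sqrt(231/345), the second weight has to be sqrt(114/345), not 1 − w1.

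**Levels.** The critical value at the final analysis depends on the correlation between the interim and final statistics, and in a combination test the weights fix that correlation. If the weights use 345 events, the final level must use 345 as well.

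This is the confirmatory test of a primary endpoint. The text does not define a statistic that matches its own critical values. Depending on how a statistician resolves it, the test loses power or exceeds the OS alpha.

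**Working it through.** **Inputs (protocol synopsis, Sections 11.2, 11.2.2 and 11.5.1).** 231 OS events at IA2; 298 minimum and 393 maximum at the final analysis; 345 for the weights; overall two-sided OS alpha 0.049 or 0.05; IA2 levels 0.021/0.022; final levels 0.043/0.044; HR 0.7.

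**1. Reproducing the stated levels.** Two-sided O'Brien-Fleming-type spending at information fraction t is 4·[1 − Φ(z(1−α/4)/√t)]. The final level then solves 2·[1 − Φ₂(c1, c2; ρ)] = α with ρ = √t, where Φ₂ is the bivariate normal distribution function.

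| Fraction | ρ | IA2 level (α 0.049 / 0.05) | Final level (α 0.049 / 0.05) |
|---|---|---|---|
| 231/298 | 0.880 | 0.0213 / 0.0218 | 0.0427 / 0.0436 |
| 231/345 | 0.818 | 0.0120 / 0.0123 | 0.0453 / 0.0462 |

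The first row rounds to all four stated levels, so they were derived for 298 events. The second row matches none of them. Keeping IA2 at 0.021/0.022 and using ρ = sqrt(231/345) gives final levels of 0.03987/0.04031.

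**2. The weights.**
- w = sqrt(231/345) = 0.8183 and 1 − w = 0.1817.
- w² + (1−w)² = 0.6696 + 0.0330 = 0.7026, so the SD is 0.8382.
- Correlation of the printed sum with Z1: 0.8183/0.8382 = 0.976.
- Second weight needed for unit variance: sqrt(1 − 231/345) = sqrt(114/345) = 0.5748.

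The stated levels need a correlation of 0.880. The printed weights give 0.976 and unit-norm weights on 345 events give 0.818.

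**3. Error and power.** Let s = sqrt(w1² + w2²) and ρ = w1/s.
- Overall error = 2·[1 − Φ₂(c1, c2/s; ρ)].
- Power = 1 − Φ₂(c1 − m1, (c2 − w1·m1 − w2·m2)/s; ρ), with m1 = |ln 0.7|·√231/2 = 2.711 and m2 = |ln 0.7|·√(D − 231)/2. Here m2 = 1.460 at D = 298 and 2.270 at D = 393.

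| Test (IA2 level 0.021) | Final level | Overall error (limit 0.049) | Power, 298 events | Power, 393 events |
|---|---|---|---|---|
| Printed weights, taken literally | 0.043 | 0.0231 | 72.0% | 76.8% |
| Printed sum divided by its SD | 0.043 | 0.0437 | 82.6% | 86.8% |
| w read as the squared weight | 0.043 | 0.0479 | 85.7% | 91.9% |
| Unit-norm on 345, stated level kept | 0.043 | 0.0517 | 86.4% | 93.5% |
| Unit-norm on 345, level recomputed | 0.0399 | 0.049 | 85.8% | 93.1% |

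In the other scenario (0.022/0.044, limit 0.05), unit-norm weights on 345 events with the stated levels give 0.0532. A simulation of 4 million draws agreed: literal error 0.0232; unit-norm error at the stated levels 0.0519 and 0.0533; literal power 72.1% and 76.8%.

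**4. Loss from the printed form.** Against the consistent test the literal reading loses 85.8 − 72.0 = 13.8 points at 298 events and 93.1 − 76.8 = 16.3 at 393. Going from 298 to 393 events gains 76.8 − 72.0 = 4.8 points as printed and 93.1 − 85.8 = 7.3 in the consistent test.

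**The case against.** The strongest reply is that 1 − w is a slip of notation. The cited combination method and the reference to a correlation both suggest a standardised statistic. A misplaced radical would explain the text: with w = 231/345, the weights sqrt(w) and sqrt(1−w) are correct. On the milder readings in the table the loss runs from under 1 to about 6 points, and no reading of the printed weights exceeds the OS alpha. That is fair, and the 72% figure applies only to the literal reading. But the visible text neither rescales the sum nor calls w a squared weight, and the same formula stands in two places. Even the misplaced-radical explanation leads to unit-norm weights on 345 events, where 0.043/0.044 are too lenient.

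Second, Section 11.2.2 says the levels apply to the planned event counts and will be adjusted if actual counts differ. This does not help. The mismatch exists at the planned counts, and the weights fix the correlation whatever the final count turns out to be.

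Third, not everything is visible. The testing-procedure figure is not shown, part of the statistical section is redacted, and the SAP calls itself an update, so fuller details may exist elsewhere. That limits the statement to the documents at hand. The SAP supplied corrects neither point.

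Fourth, the trial stopped and no OS test will be run. That is true, and it removes any effect on results, but not the error in the protocol.

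**Conclusion.** The concern holds on both counts. The printed weights give a null variance of 0.703, and the stated levels were derived for 298 events while the weights use 345. As a specification of the confirmatory OS test this must be corrected.

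Taken literally, the test is conservative (0.023 against 0.049) and loses about 14 to 16 points of power at HR 0.7. If only the weights are corrected, the error exceeds its limit by about 0.003 in each scenario.

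These figures assume independent increments, Z1 at exactly 231 events, fixed final totals of 298 or 393, and levels 0.021/0.043 for power. Power under the adaptive rule was not computed, because Section 11.2.2 places that rule in a DMC Charter appendix that was not supplied.

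**What to change.** In the synopsis and Section 11.5.1, define the final statistic as Z = sqrt(231/345)·Z1 + sqrt(114/345)·Z2, compared with the standard normal. Z1 is the stratified log-rank statistic at IA2 and Z2 is the independent increment after IA2.

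In the synopsis and Sections 11.2.2 and 11.5.1, replace 0.043/0.044 by levels computed from these weights. With IA2 kept at 0.021/0.022, the exact values are 0.03987 (ORR not significant) and 0.04031 (ORR significant). Rounded down to stay within alpha, these are 0.0398 and 0.0403. State that the IA2 spend is based on 231/298.

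An equally valid repair is to build the weights on 298 events, sqrt(231/298) and sqrt(67/298), and keep the stated levels. The overall error is then 0.0491 and 0.0505 with the rounded levels, so unrounded levels should be used. Power is 86.1% at 298 events and 92.6% at 393.

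The cost is a change of wording and one boundary calculation. The stricter final level costs about 0.6 points of power at 298 events (86.4% to 85.8%) compared with keeping 0.043. No patients or data are added.

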## 1.1 Study Schematic

Figure 1: Study Schematic

Abbreviations: ~ = approximately; CPS = combined positive score; DMC = Data Monitoring Committee; HNSCC = head and neck squamous-cell carcinoma; HPV = human papillomavirus; IV = intravenous; ORR = objective response rate; OS = overall survival; PD = progressive disease; PD-L1 = programmed cell death ligand 1; q3w = every 3 weeks; RR = randomization ratio

Note: The study schematic describes the initial treatment (ie, First Course). See Section 6.2.6 for information regarding eligibility for a Second Course.

a. Additional reasons for discontinuing imaging are withdrawal of consent and the end of the study (see Section 8.1.2).

1.2 Schedule of Events

Table 1: Schedule of Events (Excluding Pharmacokinetic, Immunogenicity, ██████████ Sampling)

Procedure / Period:	Screening	Treatment Cycles (3-Week Cycles)					Post-treatment		
		Cycle 1 Only			Cycle 2 and Beyond		Follow-up Visit 1 y	Follow-up Visit 2 y	Survival Follow-up z
Study Days a :	Day -28 to -1	Day 1	Day 3 (- 1 day)	Phase 3 only: Day 5 (± 1 day)	Day 1 (± 3 days)	Day 3 (+ 2 days)	30 days from last dose (± 7 days)	90 days from last dose (± 7 days)	Every 12 weeks (± 14 days)
Informed consent	X								
Inclusion/ exclusion criteria	X								
Demographics and medical history b	X								
Tumor biopsy c	X								
Randomization		X d							
Physical examination e	X	Predose			Predose		X	X	
Vital signs f	X	X f	X		X f		X	X	
ECOG performance status g	X	Predose			Predose		X	X	
ECG h	X								
ECHO/MUGA i	X								
Pregnancy test j	X j	Predose j			Predose		X	X	
Hematology and serum chemistry k	X	Predose			Predose		X		
Coagulation k	X								
Thyroid function tests (T3 [total or free], free T4, TSH) l	X				Predose l		X		

**Table 1: Schedule of Events (Excluding Pharmacokinetic, Immunogenicity, [REDACTED] Sampling) (Contd)**

Procedure / Period:	Screening	Treatment Cycles (3-Week Cycles)					Post-treatment		
		Cycle 1 Only			Cycle 2 and Beyond		Follow-up Visit 1 y	Follow-up Visit 2 y	Survival Follow-up z
Study Days a :	Day -28 to -1	Day 1	Day 3 (-1 day)	Phase 3 only: Day 5 (± 1 day)	Day 1 (± 3 days)	Day 3 (+ 2 days)	30 days from last dose (± 7 days)	90 days from last dose (± 7 days)	Every 12 weeks (± 14 days)
Additional lab assessments m	X				Pre-dose m				
Urinalysis (dipstick) n	X	Pre-dose			Pre-dose				
Serology o	X								
Tumor HPV status p	X								
PK and immunogenicity assessments		Phase 2 portion of the study: refer to Table 8 Phase 3 portion of the study: refer to Table 9							
[REDACTED]		[REDACTED]							
Tumor assessment q	X	First year from date of randomization, imaging every 6 weeks (± 7 days), or more frequently if clinically indicated. After 1 year from randomization, imaging every 9 weeks (± 14 days) for patients who remain on treatment.				For patients who discontinue study drug without progression, monitor every 6 weeks (± 7 days) (or every 9 weeks ± 14 days 1 year after randomization) until: 1) Start of new anticancer treatment, 2) Disease progression by BICR, 3) Death, 4) Withdrawal of consent, or 5) End of the study, whichever occurs first. The first follow-up assessment should occur 6 weeks (± 7 days) from the last scheduled on-treatment imaging time point (or 9 weeks ±14 days from the last scheduled on-treatment imaging time point 1 year after randomization).			

**Table 1: Schedule of Events (Excluding Pharmacokinetic, Immunogenicity, [REDACTED] Sampling) (Contd)**

Procedure / Period:	Screening	Treatment Cycles (3-Week Cycles)					Post-treatment		
		Cycle 1 Only			Cycle 2 and Beyond		Follow-up Visit 1 y	Follow-up Visit 2 y	Survival Follow-up z
Study Days a :	Day -28 to -1	Day 1	Day 3 (-1 day)	Phase 3 only: Day 5 (± 1 day)	Day 1 (± 3 days)	Day 3 (+ 2 days)	30 days from last dose (± 7 days)	90 days from last dose (± 7 days)	Every 12 weeks (± 14 days)
Arm A (bempegaldesleukin plus pembrolizumab) only:									
Local lab assessments prior to dosing f		Predose			Predose				
Administer IV fluids s		X			X				
Premedications t		Predose			Predose				
Oral hydration follow-up			X u			X u			
Study drug administration v		X			X				
AE assessment	X	At every visit					X	X	
Review of concomitant medications/procedures	X	At every visit					X	X	
Health-related quality of life assessments w		Predose			Predose		X		
Subsequent anticancer therapy x							X	X	X
Follow-up visits y							X	X	
Survival follow-up z									X

Abbreviations: AE = adverse event; BICR = blinded independent central review; ctDNA = circulating tumor deoxyribonucleic acid; ECG = electrocardiogram; ECHO = echocardiogram; ECOG = Eastern Cooperative Oncology Group; EQ-5D = EuroQol EQ-5D questionnaire; HPV = human papillomavirus; IV = intravenous; min = minutes; MUGA = multigated acquisition; PD-L1 = programmed cell death ligand 1; PK = pharmacokinetics; T3 = triiodothyronine; T4 = thyroxine; TSH = thyroid-stimulating hormone.

- a. Cycle intervals less than 21 days (eg, 21 days - 3 days) should only occur if the Investigator believes there are no safety concerns with dosing the patient 1 to 3 days prior to a 21-day cycle. All procedures and examinations should be performed before the administration of study drug(s), except as indicated. If scheduled visits or assessments coincide with a weekend or holiday, schedule at the next feasible date. Please contact the Medical Monitor to discuss any concerns about study visits or assessments that may fall out of the protocol-specified window because of unforeseen delays, the coronavirus disease 2019 (COVID-19) public health emergency, or other patient-specific circumstances. All out of window visits and procedures will incur a protocol deviation. Following randomization, Investigators may choose to perform study visits via telemedicine or at alternate locations if needed during periods of global pandemics (eg, COVID-19); however, any protocol-mandated procedures that cannot be performed via telemedicine or at alternate locations will be documented as a protocol deviation.
- b. A medical history will be obtained by the Investigator or qualified designee. Medical history will include all active conditions, and any condition diagnosed within the prior 10 years that is considered to be clinically significant by the Investigator. The patient's history of tobacco use will also be collected. Details regarding the patient's head and neck cancer will be recorded separately and not listed as medical history.
- c. **Tumor tissue requirements:** formalin-fixed paraffin-embedded (FFPE) tumor tissue block (obtained within 12 months of randomization) or unstained FFPE tumor tissue sections on slides (a minimum of 8 slides, preferably 15 to 25, obtained within 4 months [if stored in the dark at room temperature up to 25°C] or 6 months [if stored in the dark at 2°C–8°C] of randomization) collected from a recurrent lesion without intervening therapy and irradiation, are acceptable in lieu of a newly obtained excisional, incisional, or core tumor biopsy prior to treatment. Recurrent lesions in a previously irradiated area can be biopsied if progression has been shown in such lesions since irradiation. See Section 8.3.1. Newly obtained biopsies are preferred to archived tissue.  
**PD-L1 expression:** PD-L1 expression testing will be determined by a local or central laboratory. PD-L1 testing will use the PD-L1 IHC 22C3 PharmDx diagnostic kit.
- d. Within 5 calendar days following randomization, the patient should receive the first dose of study treatment.
- e. Physical examinations must occur within 5 days prior to administering study drug(s). A full physical examination should be conducted during Screening; targeted physical examinations should be conducted on Day 1 of Cycles 1 and beyond and at the post-treatment follow-up visits. See Section 10.19 for additional details.
- f. See Section 10.20. Weight is to be reported at each vital sign visit, height at screening only. On dosing days, vital signs are to be taken and recorded as follows:
  - **For Arm A (bempegaldesleukin/pembrolizumab):** prior to bempegaldesleukin infusion and 30 ( $\pm$  10) minutes following the end of pembrolizumab infusion.
  - **For Arm B (pembrolizumab monotherapy):** prior to pembrolizumab infusion and 30 ( $\pm$  10) minutes following the end of pembrolizumab infusion.
- g. ECOG performance status assessments for Day 1 of each cycle must occur within 5 days prior to administering study drug(s) (see Appendix 3). If the Cycle 1 Day ECOG assessment will be performed within 7 days of the Screening assessment, the ECOG assessment will not need to be repeated.
- h. ECG must be done within 14 days of the date of randomization. See Section 10.21.
- i. A standard echocardiogram or MUGA must be performed for all patients within 60 days prior to randomization to assess for cardiac function and left ventricular ejection fraction (LVEF). See Section 10.22.
- j. Pregnancy test information is provided in Section 10.16.1. Women of childbearing potential (WOCBP) must have a screening negative serum or urine pregnancy test within 28 days prior to randomization. A negative highly sensitive pregnancy test (urine or serum as required by local regulations) is required within 24 hours for urine or within 72 hours for serum before the first dose of study treatment.
- k. Screening hematology and chemistry and coagulation must be drawn within 10 days of the date of randomization. Hematology and chemistry assessments for Day 1 of each cycle must be drawn within 5 days prior to administering study drug(s). See Section 10.18 and Appendix 1.

- l. See [Appendix 1](#). Screening thyroid function tests must be drawn within 28 days of the date of randomization. Thyroid function tests may be obtained within 5 days of administration of study drugs.
- m. See [Appendix 1](#). Screening additional laboratory tests must be drawn within 28 days of the date of randomization. For Cycle 2 and beyond, the sampling for additional laboratory tests can be drawn within 5 days prior to administration of study drug(s). Any patient receiving anticoagulant therapy should have coagulation factors monitored closely throughout the study via local laboratories per institutional guidelines.
- n. See [Appendix 1](#). Urinalysis assessment for Day 1 of each cycle must be provided within 5 days prior to administering study drug(s).
- o. Screening serology laboratory tests can be drawn within 28 days of the date of randomization. See [Appendix 1](#).
- p. For patients with oropharyngeal cancer only: tumor tissue collection for HPV status is described in [Section 8.3.1.1](#).
- q. [Section 8.1](#) describes tumor imaging (including confirmation of tumor response) and assessment of disease. All tumor assessments will be sent to the imaging vendor. For patients who continue to receive treatment beyond progression, see [Section 6.2.5](#). For assessments in long-term follow-up, see [Section 6.3](#).

